3.2. Detailed analysis proposal

3.2.1. Descriptive component:

The following tables show how the results of the descriptive component of the analysis will be reported, according to the different variables considered in the study:

Table 1Demographic variables

Variable	HDx	HF-HD	Total
Sex			
Male	n(%)	n(%)	n(%)
Female	n(%)	n(%)	n(%)
		Mean (SD), Median	Mean (SD), Median
Age	Mean (SD), Median (IQR)	(IQR)	(IQR)
Ethnicity			
Indigenous	n(%)	n(%)	n(%)
African American	n(%)	n(%)	n(%)
Mestizo	n(%)	n(%)	n(%)
City			
1	n(%)	n(%)	n(%)
2	n(%)	n(%)	n(%)
3	n(%)	n(%)	n(%)
4	n(%)	n(%)	n(%)
5	n(%)	n(%)	n(%)
6	n(%)	n(%)	n(%)
7	n(%)	n(%)	n(%)
Insurer			
1	n(%)	n(%)	n(%)
2	n(%)	n(%)	n(%)
3	n(%)	n(%)	n(%)
4	n(%)	n(%)	n(%)
5	n(%)	n(%)	n(%)
Kidney clinic			
1	n(%)	n(%)	n(%)
2	n(%)	n(%)	n(%)
3	n(%)	n(%)	n(%)
4	n(%)	n(%)	n(%)
5	n(%)	n(%)	n(%)
6	n(%)	n(%)	n(%)
7	n(%)	n(%)	n(%)
8	n(%)	n(%)	n(%)
9	n(%)	n(%)	n(%)
10	n(%)	n(%)	n(%)
11	n(%)	n(%)	n(%)
12	n(%)	n(%)	n(%)

Table 2Medical history variables

Variable	HDx	HF-HD	Total
Seniority in dialysis	Median (IQR)	Median (IQR)	Median (IQR)
Etiology of CKD			
1= Hypertension	n(%)	n(%)	n(%)
2= Diabetes			
mellitus	n(%)	n(%)	n(%)
3= Autoimmune			
glomerular	n(%)	n(%)	n(%)
4= Obstructive	n(%)	n(%)	n(%)
5= Disease			
polycystic	n(%)	n(%)	n(%)
6= Unknown	n(%)	n(%)	n(%)
7= Other	n(%)	n(%)	n(%)
Dx Hypertension	n(%)	n(%)	n(%)
Dx Diabetes	n(%)	n(%)	n(%)
Dx Cardiovascular			
Disease	n(%)	n(%)	n(%)
Charlson index	Median (IQR)	Median (IQR)	Median (IQR)
Karnofsky	Median (IQR)	Median (IQR)	Median (IQR)
Urine (diuresis			
ml/day)			
< 100 ml/day	n(%)	n(%)	n(%)
100 to 400			
ml/day	n(%)	n(%)	n(%)
>400 ml/day	n(%)	n(%)	n(%)

Table 3. 3

Variable	HDx	HF-HD	Total
Duration of weekly sessions, hours	Median (IQR)	Median (IQR)	Median (IQR)
Dialyzer	n(%)	n(%)	n(%)
QD	Median (IQR)	Median (IQR)	Median (IQR)
QB	Median (IQR)	Median (IQR)	Median (IQR)
PHEW	Median (IQR)	Median (IQR)	Median (IQR)
Type of access			
1= Temporary catheter	n(%)	n(%)	n(%)
2= Catheter tunneled	n(%)	n(%)	n(%)
3= Native FAV	n(%)	n(%)	n(%)
4= AVF graft	n(%)	n(%)	n(%)
Anticoagulant			
1= Heparin	n(%)	n(%)	n(%)
2= Heparin LMW	n(%)	n(%)	n(%)
3= Not used	n(%)	n(%)	n(%)
Dose anticoagulant	Median (IQR)	Median (IQR)	Median (IQR)
TA_Systolic pre	Median (IQR)	Median (IQR)	Median (IQR)
TA_Pre- diastolic	Median (IQR)	Median (IQR)	Median (IQR)
Post Systolic BP	Median (IQR)	Median (IQR)	Median (IQR)
TA_Post diastolic	Median (IQR)	Median (IQR)	Median (IQR)

Table 4Laboratory parameter variables

Variable	HDx	HF-HD	Total
Albumin	Mean (SD), Median	Mean (SD), Median	Mean (SD), Median
Albumin	(IQR)	(IQR)	(IQR)
PTHi	Mean (SD), Median	Mean (SD), Median	Mean (SD), Median
PINI	(IQR)	(IQR)	(IQR)
Phosphorus	Mean (SD), Median	Mean (SD), Median	Mean (SD), Median
Pilospilorus	(IQR)	(IQR)	(IQR)
Calcium	Mean (SD), Median	Mean (SD), Median	Mean (SD), Median
Calcium	(IQR)	(IQR)	(IQR)
Potassium	Mean (SD), Median	Mean (SD), Median	Mean (SD), Median
Potassium	(IQR)	(IQR)	(IQR)
Homoglobin	Mean (SD), Median	Mean (SD), Median	Mean (SD), Median
Hemoglobin	(IQR)	(IQR)	(IQR)
Platelets	Mean (SD), Median	Mean (SD), Median	Mean (SD), Median
Piateiets	(IQR)	(IQR)	(IQR)
Lymphocytos	Mean (SD), Median	Mean (SD), Median	Mean (SD), Median
Lymphocytes	(IQR)	(IQR)	(IQR)
lron	Mean (SD), Median	Mean (SD), Median	Mean (SD), Median
Iron	(IQR)	(IQR)	(IQR)
Ferritin	Mean (SD), Median	Mean (SD), Median	Mean (SD), Median
remun	(IQR)	(IQR)	(IQR)
SATT	Mean (SD), Median	Mean (SD), Median	Mean (SD), Median
SAII	(IQR)	(IQR)	(IQR)
TIBC	Mean (SD), Median	Mean (SD), Median	Mean (SD), Median
TIBC	(IQR)	(IQR)	(IQR)
PCRHS	Mean (SD), Median	Mean (SD), Median	Mean (SD), Median
PCNII3	(IQR)	(IQR)	(IQR)
BUN pre	Mean (SD), Median	Mean (SD), Median	Mean (SD), Median
boly pre	(IQR)	(IQR)	(IQR)
BUNpost	Mean (SD), Median	Mean (SD), Median	Mean (SD), Median
вомрозі	(IQR)	(IQR)	(IQR)
Kt/V	Mean (SD), Median	Mean (SD), Median	Mean (SD), Median
Kt/ V	(IQR)	(IQR)	(IQR)
Cholesterol	Mean (SD), Median	Mean (SD), Median	Mean (SD), Median
Cholesteroi	(IQR)	(IQR)	(IQR)
HDL	Mean (SD), Median	Mean (SD), Median	Mean (SD), Median
IIDL	(IQR)	(IQR)	(IQR)
LDL	Mean (SD), Median	Mean (SD), Median	Mean (SD), Median
LDL	(IQR)	(IQR)	(IQR)
Triglycarides	Mean (SD), Median	Mean (SD), Median	Mean (SD), Median
Triglycerides	(IQR)	(IQR)	(IQR)

Table 5Medication variables

Variable	HDx	HF-HD	HF-HD
Nutritional supplements yes	n(%)	n(%)	n/ 9/)
or no	11(/0)	11(/0)	n(%)
Type of supplement			
1=Full formula	n(%)	n(%)	n(%)
2=Specialized complete	n/ 9/)	n/ 0/\	n/ 9/)
formula	n(%)	n(%)	n(%)
1=Modular formula	n(%)	n(%)	n(%)

^{*}Variables measured every 6 months

Table 6variables *

Variable	HDx	HF-HD	HF-HD
BMI	Mean (SD),	Mean (SD),	Mean (SD), Median
	Median (IQR)	Median (IQR)	(IQR)
Categorized BMI			
1= Underweight	n(%)	n/ 9/)	n/ 9/)
(<18.5)	11(/0)	n(%)	n(%)
2 = Normal (18.5 –	n/ 0/\	n/ 0/\	n/ 0/)
24.9)	n(%)	n(%)	n(%)
3 = Overweight (25.0 –	n(%)	n/ 9/)	n(%)
29.9)	11(70)	n(%)	11(70)
4= Obesity (>=30)	n(%)	n(%)	n(%)
PEW	Mean (SD),	Mean (SD),	Mean (SD), Median
	Median (IQR)	Median (IQR)	(IQR)
PEW categorized			
0=No wear (0-2)	n(%)	n(%)	n(%)
1=With wear (>=3)	n(%)	n(%)	n(%)
Malnutrition-			
Inflammation Scale			
Hydration status			
0= No signs and	n/ 9/)	n/ 9/)	n/ 0/)
symptoms	n(%)	n(%)	n(%)
1=Edema below the	n/ 9/)	n/ 9/)	n/ 0/)
knees	n(%)	n(%)	n(%)
2=Edema above knees	n(%)	n(%)	n(%)

Karnofsky	Mean (SD),	Mean (SD),	Mean (SD), Median
	Median (IQR)	Median (IQR)	(IQR)
Nutritional assessment			
1	n(%)	n(%)	n(%)
2	n(%)	n(%)	n(%)
3	n(%)	n(%)	n(%)

^{*}Variables measured every 6 months

Table 7Hospitalization variables

Variable	HDx	HF-HD	HF-HD
Hospitalization yes	n(%)	n(%)	n(%)
or no	11(70)	11(70)	11(70)
Diagnosis in			
hospitalization			
1=Cat 1	n(%)	n(%)	n(%)
2=Cat2	n(%)	n(%)	n(%)
3=Cat3	n(%)	n(%)	n(%)
Major			
cardiovascular	n(%)	n(%)	n(%)
event yes or no			
Fatal cardiovascular	n(%)	n/ 0/)	n(%)
event yes or no	11(70)	n(%)	11(70)
COVID in	n(%)	n(%)	n(%)
hospitalization	11(70)	11(/0)	11(70)
Days of hospital	Mean (SD), Median	Mean (SD), Median	Mean (SD), Median
stay	(IQR)	(IQR)	(IQR)

Table 8Mortality variables*

	HDx	HF-HD	Total
Death yes or no	n(%)	n(%)	n(%)
Cause of death			
1=Cancer	n(%)	n(%)	n(%)
2= Cardiovascular	n(%)	n(%)	n(%)
3=Infectious	n(%)	n(%)	n(%)
4=Metabolic	n(%)	n(%)	n(%)
5=Respiratory	n(%)	n(%)	n(%)
6 = COVID	n(%)	n(%)	n(%)

7=Other	n(%)	n(%)	n(%)
8= Unknown	n(%)	n(%)	n(%)
Dialysis-related death yes or no	n(%)	n(%)	n(%)

^{*}Variables measured every 6 months

Table 9End-of-follow-up variables*

	HDx	HF-HD	Total
Reason for			
termination of			
follow-up			
1= Death	n(%)	n(%)	n(%)
2= Loss of tracking	n(%)	n(%)	n(%)
3= Change of			
health	n(%)	n(%)	n(%)
provider/insurer			
4= Recover kidney	n(%)	n(%)	n(%)
function	11(70)		
5= Suspension of	n(%)	n(%)	n(%)
treatment			
6= Transplant	n(%)	n(%)	n(%)
7= Dialyzer change	n(%)	n(%)	n(%)
8= Changed to DP	n(%)	n(%)	n(%)
9= End of study	n(%)	n(%)	n(%)

^{*}Variables measured every 6 months

4. Data extraction and preparation

After the measurement of variables and the collection of data are completed, the sponsor of the study must provide the analysis group with a file containing the results of the measurements of the variables considered in the project. It is recommended that this file be in a plain text format, preferably as comma-separated text (*. csv) or tab-separated text (*. txt). Additionally, the sponsor is required to provide a file with the variable dictionary that must contain the following information:

- For continuous variables and outcome-related variables: The names of the
 variables considered in the database, the labels for each variable, and the values
 corresponding to the lower and upper ends of the range must be included.
- 2. For ordinal variables: Names of the variables included in the database, labels for each variable, labels for the categories of each variable, and the values corresponding to the lower and upper ends of the range.
- 3. For nominal variables: Names of the variables included in the database, labels for each variable, and labels for the categories of each variable.
- 4. Dates included in the database must be recorded consistently, using a single format for the entire database.
- 5. The database must contain an identification code for each patient to ensure the anonymity of the information provided by the participants.

After having received the database and the variable dictionary to their satisfaction, the personnel in charge of the analysis will sign a confidentiality agreement.

Subsequently, the group of data analysts will carry out the following activities:

- 1. Importing data into the Stata® program.
- 2. Creating a working copy of the original database.
- 3. Using the working copy, verify both the integrity of the database and the names and labels of variables and categories.
- 4. Using the working copy, quality check of the database: For each variable, a review of missing values and consistency of information will be carried out.

Any problems detected in the above activities will be reported to the sponsor of the study, so that the information in the original source of the data can be reviewed and the necessary corrections can be made to ensure the quality and validity of the database.

All stages related to the extraction and preparation of the database will be documented in a *.do file within the Stata® program.

5. Preliminary analysis and draft report

Once the statistical analyses have been completed, the results will be presented in tabular and graphical formats. These preliminary results will be delivered in an editable Word file, as a draft report. As additional material, *.do files will be delivered with documentation of the database recruitment and analysis processes. Based on the results of the review of the draft report, the sponsor of the study may propose additional analyses.

6. Final analysis and results report

Based on the recommendations resulting from the previous stage, it may be necessary to perform new analyses or to expand existing ones. In this case, the new results will be included in the final report of the statistical analysis plan. This last phase has the following products:

- 1. Delivery of the original database.
- 2. Delivery of the working databases, appropriately validated and labeled, in Stata format.
- 3. Delivery of database preparation documentation files and statistical analysis files in *.do format.
- **4.** Delivery of a final report, in Word format, with the results of the analyses carried out.

7. Schedule

The following table presents the estimated duration for each of the processes related to statistical analysis:

Task	Timeline
Data extraction and preparation of	3 weeks
databases	
Preliminary analysis and draft report	2 weeks
Review by the sponsor	1 week
Final analysis and results report	3 weeks

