2.4. Primary Outcomes

Incidence of hospitalization events (per patient-year)

- Length of hospitalization (hospital days per patient-year)
- Mortality
- 4-year survival

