⁵Austin PC, Stuart EA. (2017) The Performance of Inverse Probability of Treatment Weighting and Full Matching on the Propensity Score in the Presence of Model Misspecification When Estimating the Effect of Treatment on Survival Outcomes. Stat Methods Med Res, 26(4), 1654-1670

- 4. Evaluation of the balance of covariates: It will be carried out with graphical methods (QQ plots for continuous variables and bar graphs for nominal variables), and with descriptive numerical methods (standardized mean differences and variance ratios) and inferential methods (t tests and rank sum tests) ⁶.
- 5. Estimation of treatment effect: Treatment effects, according to the type of outcome, will be estimated using generalized linear models with weighting of the observations in the sample ⁷.
- 6. Sensitivity analysis: This analysis will be performed to determine the magnitude of the bias that may be produced by the omission of covariates. For this analysis, the methodology proposed by Carnegie, Harada, Dorie and Hill will be used ⁸.

In accordance with the specific objectives set out in the protocol, the following types of analysis are proposed:

- 1. For the objectives related to the comparison of time to hospitalization and time to death event between both cohorts, the respective incidence rates for each group and the survival functions will be calculated using Kaplan-Meier estimators.
 Comparisons between the survival functions of each of the two groups will be made with log- rank, Tarone-Ware or Peto-Peto Prentice tests, depending on the censoring pattern. Additionally, Cox models will be used to estimate the strength of association between type of treatment and time to event using the HRs metric.
 In these models, weighted samples will be used with the IPTW method and a group of time-dependent covariates will be incorporated (serum albumin, PEW, MIS, hs CRP, type of dialyzer).
- 2. To meet the objectives related to counting variables (days of hospitalization and non-fatal cardiovascular events), Poisson regression models or negative binomial

⁶Austin P.C. (2009) Balance diagnostics for comparing the distribution of baseline covariates between treatment groups in propensity-score matched samples. Stat Med 10;28(25):3083-107

⁷Austin P.C. (2016) Variance Estimation When Using Inverse Probability of Treatment Weighting (IPTW) With Survival Analysis. Stat Med. 35 (30), 5642-5655

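### Follow-up ends at suspension of treatment and the mortality analysis has no rule for these patients, so 4-year survival is overstated if they die faster than those still followed

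*SAP*

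**What the plan says.** Section 2.4 names mortality and "4-year survival" among the primary outcomes.

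In section 3.2.1, the table titled "Table 9End-of-follow-up variables" gives nine reasons for ending follow-up. Code 5 is "5= Suspension of" treatment. Death is code 1, loss of tracking code 2, and transplant code 6. Recovery has its own code ("4= Recover kidney" function), and so does peritoneal dialysis ("8= Changed to DP").

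For time to death, the first item in section 3.1.2.2's list of analyses by objective says that "the survival functions will be calculated using Kaplan-Meier estimators". It adds rank tests and Cox models with inverse probability of treatment weights. Censoring is mentioned there only as a guide to choosing the rank test: "Tarone-Ware or Peto-Peto Prentice tests, depending on the censoring pattern".

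**The concern.** Kaplan-Meier and Cox methods read a censored patient as having the same later risk of death as comparable patients still under observation. Code 5 is not defined. By elimination, it covers patients whose treatment stopped without recovery, transplant or a change to DP. For a dialysis cohort, equal later risk is a doubtful assumption for such patients, and the event that may be missed is the primary outcome itself.

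The SAP's existing tools are aimed elsewhere. The treatment weights deal with assignment to dialyzer. The sensitivity analysis in step 6 of section 3.1.2.2 deals with omitted covariates. The section on missing data deals with imputing variables. There is no rule for vital status after exit, no censoring weight and no analysis of informative censoring in the mortality comparison.

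At stake are the 4-year survival figures for both cohorts and, under an extra condition, the hazard ratio between them.

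**Working it through.** **Step 1: what follows from the text.** Table 9 ends follow-up at code 5 and keeps death apart as code 1. The methods for time to death use follow-up time and an event indicator. A patient who leaves at code 5 alive, with no later death carried into the analysis, contributes a censored time. The SAP does not say this in words; it follows from the two places read together.

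**Step 2: inputs.** The SAP gives no death rate, no suspension rate and no survival after suspension, so there is no figure of its own to reproduce. All rates below are assumptions:
- h, death hazard while followed: 0.12 per year (range 0.08 to 0.16)
- w, suspension rate: 0.005, 0.01 or 0.02 per year (range up to 0.04)
- q, fraction dying promptly after suspension, the rest continuing at hazard h: 1 (range 0.5 to 1)

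The 4-year horizon is from section 2.4.

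**Step 3: 4-year survival.** Censoring at suspension estimates exp(−4h). All-cause survival is exp(−4(h + q·w)). With h = 0.12, the censored estimate is exp(−0.48) = 61.9%. With q = 1:

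| w per year | All-cause survival | Overstatement | Share of deaths missed, w/(h + w) |
|---|---|---|---|
| 0.005 | exp(−0.50) = 60.7% | 1.2 points | 0.005/0.125 = 4% |
| 0.01 | exp(−0.52) = 59.5% | 2.4 points | 0.01/0.13 = 8% |
| 0.02 | exp(−0.56) = 57.1% | 4.8 points | 0.02/0.14 = 14% |

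With q = 0.5 the overstatement is 0.6, 1.2 and 2.4 points. Over h = 0.08 to 0.16, w = 0.005 to 0.04 and q = 0.5 to 1, it runs from 0.5 to 10.7 points.

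**Step 4: hazard ratio.** Assume hazards of 0.10 (MCO) and 0.12 (HD AF). The censored ratio is 0.10/0.12 = 0.83. Counting prompt deaths after suspension (q = 1):
- equal suspension, 1% in each: 0.11/0.13 = 0.85
- 1% MCO, 2% HD AF: 0.11/0.14 = 0.79
- 2% MCO, 1% HD AF: 0.12/0.13 = 0.92

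The direction of the survival error is fixed once suspended patients die faster than the rest. The hazard ratio moves little unless suspension is uneven, and it can then move either way.

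**The case against.** The strongest reply is that the censoring is inferred. Table 9 is a shell for descriptive reporting, not a definition of events and censoring. Mortality has its own variables in Table 8, including a plain yes/no for death, and nothing says that a death after suspension is barred from it or could not be coded 1. This stands. A reader might infer that such deaths are never counted; the SAP does not establish that. A reader might also take the lack of a cause-of-death category for stopping dialysis as evidence. It is not: Table 8 has metabolic, other and unknown causes, and a cause label does not remove an event from all-cause mortality.

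Second, every rate above is assumed, and prompt death after suspension is not documented in the SAP. This also stands. It limits what can be said about size, not about direction under the stated condition.

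Third, the Cox models include time-dependent albumin, PEW, MIS and hs CRP, which may partly account for who suspends. That helps the hazard ratio somewhat. It does nothing for the Kaplan-Meier curves and does not capture deaths caused by stopping itself.

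Fourth, objective 4 compares patients receiving each therapy, so follow-up while on treatment could be deliberate. That is a defensible choice. Even so, reading a Kaplan-Meier value at 4 years as survival still requires that exits be unrelated to the risk of death.

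Finally, the SAP does not say that the registry holds vital status after exit. The fix has to allow for that.

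**Conclusion.** The point holds in a conditional form. As written, patients who leave alive at code 5 would be treated as non-informatively censored in a primary analysis, with no safeguard. If they die at a higher rate than those still followed, 4-year survival is overstated: by 1.2 to 4.8 points under h = 0.12 per year, prompt death, and suspension of 0.5% to 2% per year. If suspensions are rare, or later deaths are already captured, the error is small. The true size cannot be derived from the SAP.

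Two stronger readings are tempting and not supported. One is that the MCO versus HD AF comparison is biased; that needs suspension to differ between the cohorts, and the SAP gives no evidence either way. The other is that the association between albumin and mortality is weakened; that needs suspension to be more common at low albumin, which the SAP does not state.

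This should be changed, because it bears on a primary result and is cheap to settle. It does not invalidate the plan.

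**What to change.** In the first item of section 3.1.2.2's list of analyses by objective:

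1. State that a death recorded in the Table 8 variables after exit at code 5 counts as an event, at its date, in the mortality and 4-year survival analyses wherever the registry holds vital status. Such patients then stay at risk until death or the last date known alive.
2. Add one sensitivity analysis that counts code 5 as a death-equivalent event at the suspension date, and show it next to the primary result. If vital status after exit is unavailable, the censored and death-equivalent survival results bracket the answer, provided suspended patients die at least as fast as those still followed.

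No new count of suspensions is needed, since Table 9 already reports code 5 by cohort.

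The cost is a few lines of SAP text, use of whatever vital status the registry holds, and one extra model run. Reported survival may come out slightly lower. The death-equivalent analysis may overcount deaths if some suspended patients survive, so it should be labelled a sensitivity result and not replace the primary one.

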3.1.2.2. Multivariate analysis

Considering that the results of analyses that include effect measures may be compromised by potential confounding bias given the non-experimental design of the study, it has been

proposed that statistical models incorporate propensity score analyses using inverse probability of treatment weighting (IPTW) methods. These analyses will have the following steps:

These analyses will have the following steps 1:

- 1. Data preparation: This stage includes the selection of covariates, and the assessment of data balance and the pattern of missing data. Not only the variables that are associated with the type of dialysis and with each of the outcomes used in this research will be selected, but also those that are associated only with the outcome, since it has been reported that this decision can increase the power to evaluate the treatment effect ². In the event that the handling of missing data is required, multiple imputation methods with chained equations will be carried out, carrying out the imputation separately in each exposure group ³.
- 2. Propensity score (PS) estimation: Given the dichotomous nature of the exposure, these scores will be estimated using logistic regression methods ⁴.
- 3. Application of the PS method: As mentioned before, the IPTW method will be applied, considering that it has advantages such as sample size optimization (it does not eliminate observations that cannot be matched) and versatility for its use with different multivariate analysis methods ⁵.

¹Austin PC, Stuart EA. (2015) Moving towards best practice when using inverse probability of treatment weighting (IPTW) using the propensity score to estimate causal treatment effects in observational studies. Stat Med 10;34(28):3661-79.

²Cuong, N. V. (2013). Which covariates should be controlled in propensity score matching? Evidence from a simulation study. Statistica Neerlandica, 67(2), 169–180.

³Puma, MJ, Olsen, R.B., Bell, S.H., & Price, C. (2009). What to do when data are missing in group randomized controlled trials. Washington, DC: National Center for Education Evaluation and Regional Assistance, Institute of Education Sciences, US Department of Education.

⁴Setoguchi, S., Schneeweiss, S., Brookhart, MA, Glynn, RJ, & Cook, E.F. (2008). Evaluating uses of data mining techniques in propensity score estimation: A simulation study. Pharmacoepidemiology and Drug Safety, 17(6), 546–555.

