⁸Carnegie, N.B., Harada, M., Dorie, V., & Hill, J. (2016). treatSens: Sensitivity analysis for causal inference. Retrieved from https://cran.r-project.org/web/packages/treatSens/index.html

regression models will be used in case of overdispersion in the outcome variable. Within these models, the covariates that will be candidates for inclusion in the models are:

- a. For the outcome days of hospitalization: Serum albumin, PEW, MIS, hs CRP, dialyzer type
- 3. For non-fatal cardiovascular events outcome: Serum albumin, PEW, MIS, hs CRP, dialyzer type
- 4. For the objective related to the estimation of the association between serum albumin levels and the outcomes of mortality, non-fatal cardiovascular events, hospitalization events and days of hospital stay, the use of linear mixed models for longitudinal data is proposed. This strategy allows modeling the association between repeated measurements of independent variables and the proposed outcomes, in the presence of other variables that also vary over time. These models involve the combination of fixed effects and random effects models, and allow the inclusion of variables that change over time. To identify potential confounding variables, a directed acyclic causal diagram (DAG) will be performed. Additionally, G methods will be used for longitudinal data, which allow estimating the causal effect of an exposure that varies over time (in this case albumin levels) in the presence of confounding variables that also vary over time (hs CRP, MIS, PEW, FRR, type of dialyzer) that are in turn affected by the exposure. These methods may be more robust than traditional regression-based methods. The parametric G- formula and the weighted inverse probability of treatment estimation with marginal structural models 9will be used 10.11

⁹James M. Robins, Sander Greenland, Fu-Chang Hu. Estimation of the Causal Effect of a Time-Varying Exposure on the Marginal Mean of a Repeated Binary Outcome, J Am Stat Assoc. 1999; 94:447, 687-700.

¹⁰Miguel A Hernán, Babette Brumback, James M Robins. Marginal Structural Models to Estimate the Joint Causal Effect of Nonrandomized Treatments. J Am Stat Assoc. 2001; 96:454, 440-448.

¹¹Sally Picciotto, Miguel A. Hernán, John H. Page, Jessica G. Young, James M. Robins. Structural Nested Cumulative Failure Time Models to Estimate the Effects of Interventions. J Am Stat Assoc. 2012;107:499, 886-900.

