3.1.5. Handling missing data

Considering that in the present study data from a standardized clinical registry of proven quality in previous research will be used, a low amount of missing data is expected in the study variables. However, it is noted that the amount or pattern of missing data may affect the quality of the statistical estimates. Missing data and the mechanism by which they occur will be evaluated: MCAR (Missing Data). completely at random), MAR (Missing at random) and MNAR (Missing not at random), according to this evaluation, the appropriate data imputation procedures will be defined for each case

3.1.5 . Sample size:

Based on the availability of the assembled cohorts of 1098 patients, 564 on MCO in the Theranova® dialyzer cohort and 534 on conventional HD in the AF dialyzer cohort. This provides 90% power considering an IRR 0.82 for all-cause hospitalization and a significance level of 0.05 (26).

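### Type of dialyzer is listed as time-varying, yet a dialyzer change is listed as ending follow-up; if it does, the term cannot vary, and ending follow-up there may be informative with at most partial correction.

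*SAP*

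**What the plan says.** Three places in the SAP bear on whether a patient's dialyzer type can change within the analysed data.

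- **Section 3.1.2.2, analysis item 1 (time to hospitalization and time to death).** The Cox models estimate the hazard ratio for type of treatment in the IPTW-weighted sample, and "a group of time-dependent covariates will be incorporated (serum albumin, PEW, MIS, hs CRP, type of dialyzer").
- **Section 3.1.2.2, analysis item 4 (albumin and outcomes).** The G-methods treat serum albumin as the exposure that changes during follow-up. Type of dialyzer is then named in the list of "confounding variables that also vary over time (hs CRP, MIS, PEW, FRR, type of dialyzer) that are in turn affected by the exposure".
- **Section 3.2, Table 9.** Among the reasons why follow-up ended, beside death, transplant and end of study, stands "7= Dialyzer change".

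On censoring, the SAP says only that survival functions will be compared with "log- rank, Tarone-Ware or Peto-Peto Prentice tests, depending on the censoring pattern". The propensity score is one treatment model: "Given the dichotomous nature of the exposure, these scores will be estimated using logistic regression methods". The sensitivity analysis has a single purpose: "This analysis will be performed to determine the magnitude of the bias that may be produced by the omission of covariates". The missing-data section deals with variable values, noting that "a low amount of missing data is expected in the study variables". No censoring weights and no analysis of switching are specified.

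**The concern.** The two treatments of dialyzer type do not fit together. If a change of dialyzer closes the patient's record, every patient has one dialyzer type throughout the observed time. A time-dependent version of it in item 1 is then the treatment term under another name. In item 4 it cannot respond to later albumin, because no later value is observed. Two analysts could read the plan differently: one would compare outcomes by dialyzer at entry, the other by dialyzer in current use. These are different estimands, and the SAP does not choose between them.

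The second issue follows from the first. Item 4 describes dialyzer type as affected by albumin, and the study's premise is that albumin relates to mortality, cardiovascular events and hospitalization. If both hold, patients whose follow-up stops at a switch differ in prognosis from those who stay. Kaplan-Meier curves, the three rank tests and incidence rates all assume that this is not so. Mortality, 4-year survival and hospitalization are primary outcomes, so these comparisons carry weight.

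**Working it through.** **Step 1: consistency.** Item 1 and item 4 need at least some patients to have two dialyzer types in the data. Table 9, read as a rule, allows one per patient. Nothing else in the SAP reconciles the two.

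**Step 2: what is corrected.**

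| Analysis | Handling of a prognostic switch |
|---|---|
| Kaplan-Meier, rank tests, incidence rates | None. The censoring pattern only guides the choice of test |
| Cox model | Partial, through time-dependent albumin, PEW, MIS and hs CRP |
| Poisson or negative binomial models | The same covariates are candidates; the SAP does not say whether they are time-updated |
| IPTW, imputation, omitted-covariate analysis | None of these models the end of follow-up |

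**Step 3: possible size.** The SAP gives no switch rates and no figure to reproduce here, so every input below is assumed. Take one arm with a share p = 0.30 of high-risk patients, death hazards d_H = 0.25 and d_L = 0.08 per year, switch hazards s_H and s_L per year, and no true dialyzer effect.

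True 4-year survival: 0.30·exp(−0.25·4) + 0.70·exp(−0.08·4) = 0.110 + 0.508 = 0.619, so the true cumulative hazard is −ln 0.619 = 0.480.

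With follow-up ended at a switch, the hazard among those still observed is

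h(t) = [p·d_H·e^(−(d_H+s_H)t) + (1−p)·d_L·e^(−(d_L+s_L)t)] / [p·e^(−(d_H+s_H)t) + (1−p)·e^(−(d_L+s_L)t)].

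The Kaplan-Meier curve then estimates exp(−∫h) over 0 to 4 years. The last column divides ∫h by 0.480, which amounts to a comparison with an arm that has no informative switching.

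| s_H / s_L per year | 4-year survival as read | ∫h | Spurious ratio |
|---|---|---|---|
| Equal in both risk groups (0.10 / 0.10) | 61.9% | 0.480 | 1.00 |
| 0.05 / 0.02 | 62.3% | 0.474 | 0.99 |
| 0.15 / 0.02 | 63.6% | 0.453 | 0.94 |
| 0.30 / 0.05 | 64.8% | 0.433 | 0.90 |
| 0.30 / 0.02 | 65.1% | 0.429 | 0.89 |

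If both arms have the same prognostic switching, the ratio is 1.00 again. If the high-risk rate is 0.15 in one arm and 0.10 in the other (low-risk 0.02 in both), it is 0.453/0.463 = 0.98. If the heavy switching sits in the comparator arm, the ratio turns over: 1/0.893 = 1.12.

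The heavier rates are severe. Without deaths, 1 − exp(−0.15·4) = 45% and 1 − exp(−0.30·4) = 70% of high-risk patients would switch within 4 years.

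**Step 4: second check, by simulation with albumin that changes over time.** Assumed: 30% with low albumin at entry; each half-year 15% of low patients recover and 6% of the others become low; base death rate 0.10 per year, multiplied by 1.5, 2 or 3 when albumin is low; switch probability 0.01 per half-year except in low-albumin MCO patients; no dialyzer effect. With full follow-up the crude death-rate ratio is 1.00. With follow-up ended at the switch it is:

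| Switch probability per half-year, low-albumin MCO | Hazard ×1.5 | ×2 | ×3 |
|---|---|---|---|
| 0.05 | 0.99 | 0.99 | 0.98 |
| 0.10 | 0.98 | 0.97 | 0.96 |
| 0.20 | 0.97 | 0.95 | 0.92 |

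Both calculations concern unadjusted comparisons. Neither describes the Cox model with time-dependent covariates.

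**The case against.** The strongest reply is that Table 9 is a shell for descriptive results and states no censoring rule. Follow-up rules often sit in the protocol, which is not at hand. Table 3 also reports dialyzer as counts within each arm, so dialyzer models may differ inside an arm, and a dialyzer change could mean a change within one membrane class. This stands as far as it goes: a reader might infer a proven contradiction, and the SAP supports only a conditional one. The SAP does not draw the distinction itself, however, and its own covariate lists and table still need to be made to agree.

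A reader might also infer that the Cox analysis is uncorrected. That goes too far. Cox regression needs censoring to be non-informative given its covariates, and the four time-dependent markers in item 1 are the same ones that a censoring-weight model would use. That protection is partial: it depends on those markers explaining the switches, and it may condition on variables lying between dialyzer and outcome, which is a separate matter. The unadjusted analyses have no such protection.

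Finally, the link between albumin and switching rests on one clause in item 4, which could be a general account of when G-methods apply. No reason, rate or direction of switching is given. Switching driven by supply or clinic policy would cause little or no bias. This limits any claim about size, and the wording below keeps to that.

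**Conclusion.** The point holds in conditional form. If follow-up ends at a dialyzer change, as Table 9 indicates, dialyzer type cannot be time-varying in items 1 and 4. Ending follow-up there may also be informative, because item 4 itself has dialyzer type depend on albumin.

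The size and direction of any bias are unknown. Under assumed inputs the spurious mortality ratio runs from 1.00 through 0.99 to 0.89. The low end needs heavy switching of high-risk patients in one arm only and no covariate adjustment.

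Two stronger readings should be resisted. One is that mortality in one arm will be understated: the SAP documents no differential switching from which to conclude that. The other is to set these ratios against the planning value of 0.82. That value is an incidence rate ratio for all-cause hospitalization, a different outcome and measure from a mortality hazard ratio.

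**What to change.** 1. Define the exposure as dialyzer type at cohort entry.
2. In analysis item 1, take type of dialyzer off the time-dependent list; it is already the treatment term.
3. In analysis item 4, keep it as a baseline confounder. Dropping it altogether would conflict with specific objective 6, which requires control for type of dialyzer.
4. State whether follow-up ends at a dialyzer change, and whether a change within a membrane class counts.
5. If follow-up ends at a switch, add inverse-probability-of-censoring weights, built from time-updated albumin, hs CRP, MIS and PEW, to the survival and rate analyses.
6. Where the registry holds outcomes after a switch, add a sensitivity analysis by dialyzer at entry that follows patients on.

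The cost is revised wording, one weight model on variables already planned, and somewhat wider confidence intervals. The censoring weights need no new data. Switches by arm are already reported in Table 9, so no new table is needed.
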